No potential risks to project participants were identified.

2.3 Description of and justification for the route of administration, dosage, dosage regimen, and treatment period(s) of the modalities given to the study subjects.

'Daily Delivery and Supervision of Psychotropic Medication for High-Risk Patients with Severe and Persistent Mental Illness' is a MPAN-funded project to evaluate the effectiveness of an innovative and collaborative voluntary program for facilitating adherence to psychotropic medication after involvement with the justice system. The program involves a partnership between patients with severe and persistent mental illness and pharmacies who deliver daily dispensing services as part of their operations in hopes of improving patient outcomes such as patient wellbeing, hospitalizations and incarcerations, and in reducing costs associated with therapeutic non-adherence. Patients are supervised by pharmacy staff in their own home as they orally self-administer their regular daily medications to ensure medication compliance.

2.4 Description of the population to be studied.

Individuals with severe and persistent mental illnesses who have been repeatedly hospitalized, are repeat users of community crisis services, or are frequently in contact with the criminal justice system.

2.5 References to literature and data that are relevant to the study, and that provide background for the trial.

Angermeyer, M. C., & Matschinger, H. (2004). The stereotype of schizophrenia and its impact on discrimination against people with schizophrenia: results from a representative survey in Germany. *Schizophrenia Bulletin*, 30(4), 1049.

Canadian Institutes of Health Research. (2012). *Guide to Knowledge Translation Planning at CIHR: Integrated and End-of-grant Approaches*. Canadian Institutes of Health Research.

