
4 Study Design

The scientific integrity of the study and the credibility of the data from the study depend substantially on the study's design. A description of the study design should include:

4.1 A specific statement of the primary endpoints and the secondary endpoints, if any, to be measured during the study.

The primary endpoints to be measured during the study concern how the daily dispensing program will affect medication compliance and outcomes, hospitalizations, re-incarcerations, and community crisis utilization as

well as participants' perceptions of coercion with regards to taking part in the program and satisfaction with the program.

4.2 A description of the type/design of study to be conducted (e.g., before/after design) and a schematic diagram of study design, procedures and stages of analysis. The *before-and-after design is a reasonable option for this evaluation.*

This study proposes to employ a crossover design where data is collected for 12 months during the study and compared to baseline data retrieved for 12 months for each patient before enrollment into the project. Each patient acts as their own control. All individuals currently in the Forensics program will be asked for their informed consent to participate in the study. The study proposes to collect some personal health identifiers such as participant's personal health identification number (PHIN) and date of birth to be able to link medical records for crisis services, hospitalizations and pharmacy data. Patient names will also be collected to determine the number of contacts with criminal services. All personal identifiers will be stripped from the data for analysis and only aggregate data will be reported and/or published.

4.3 A description of the study's intervention.

The main study intervention is the daily supervision of participants while they self-administer their medications by trained pharmacy staff to ensure compliance. The staff in question will be provided by Leila pharmacy and will in addition provide support so that individuals can transition back into living independently through reminders to attend regularly scheduled medical appointments and counseling on correct use of prescribed medications.

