Leila pharmacy's LEAP program consists of 3 A'S: adherence, accessibility, and autonomy. Regarding adherence, it is common for individuals taking medications to miss doses. The LEAP program dedicates a team to help individuals living in the community to receive their medications daily at their homes. Staff will also spend some time with each individual to ensure the medications are taken appropriately. Missed or refused doses are recorded and reported back to the Leila pharmacy program coordinator.

With respect to accessibility, access to primary care is a growing problem and there are very few solutions available. This is why the Leila pharmacy team includes a nurse practitioner, dietitian, pharmacist and other allied professionals. The nurse practitioner is available to provide bridging care until a permanent family physician is available. Further, a common cause of medication discontinuation is due to the side-effects. For anti-psychotic medications, weight gain, dyslipidemia and increase risk of developing diabetes can all deter an individual from taking their medications regularly and ultimately derail them from their path to recovery. The Leila pharmacy dietitian is available to any of their clients and they can help address nutritional concerns and develop healthy meal plans. Both these services, like many others, are offered at no additional charge.

Regarding autonomy, staff respect each individual's decision and try to offer support whenever they need assistance. This is why the LEAP program is completely voluntary and their goal is be a transitional program. When an individual has made significant progress, the medical responsibilities are shifted back to the client.

5 Selection and Withdrawal of Subjects

5.1 Subject inclusion criteria.

Individuals currently enrolled in the daily dispensing program that are also part of the Forensics program and suffer from severe and persistent mental illnesses, have been repeatedly hospitalized, are repeat users of community crisis services, and/or are in frequent contact with the criminal justice system.

5.2 Subject exclusion criteria.

Individuals who are not currently in the Forensics program – those who are part of the daily dispensing program, but are not Forensic outpatients.

6 Treatment of Subjects

6.1 Procedures for monitoring subject compliance.

Participants will be visited in home on a daily basis.

7 Statistics

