7.1 A description of the statistical methods to be employed, including timing of any planned analysis(ses). Collected data would be analyzed for significant outcomes comparing before and after (a two year total time frame from pre-index date to post-index date) findings for:

- number of days/visits spent with crisis services (ED & CRC),
- hospital visits/admissions (length of stay) and
- number of incarcerations (as a dependent variable)

These data would be entered into a multivariate analysis of covariance (MANCOVA) model or similar multi-level model with baseline or study time, age and gender as the independent variables. Descriptive statistics would be used to elaborate on patient satisfaction and other variables of interest. Preliminary cost analysis will also be undertaken in anticipation of calculating a net benefit for the daily dispensing services.

7.2 The number of subjects planned to be studied.

N = 32

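### The endpoint is re-incarcerations but the analysis counts all incarcerations, so a custody episode that led to program entry can count in the baseline year only and produce an apparent fall

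*Protocol*

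**What the plan says.** Protocol 4.1 defines the primary endpoints as "how the daily dispensing program will affect medication compliance and outcomes, hospitalizations, re-incarcerations, and community crisis utilization", together with perceived coercion and satisfaction. Protocol 7.1 and the Analyses section of the SAP, in the same words, list "number of incarcerations (as a dependent variable" as the custody variable. Neither document defines an incarceration or a re-incarceration, or says whether custody that led to program entry is counted.

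Four other statements bear on the point:

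- Protocol 2.3 describes the program as "facilitating adherence to psychotropic medication after involvement with the justice system".
- Protocol 4.2 collects 12 months of study data, "compared to baseline data retrieved for 12 months for each patient before enrollment into the project", and adds "Each patient acts as their own control". There is no concurrent control.
- Protocol 5.1 takes patients who are already in both the dispensing and the Forensics programs and who have been repeatedly hospitalized, "are repeat users of community crisis services, and/or are in frequent contact with the criminal justice system".
- Protocol 7.1 speaks of "a two year total time frame from pre-index date to post-index date" without saying which event sets the index date.

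**The concern.** If a patient enters the program because of a custody episode, that episode lies before entry by construction and the follow-up year has no counterpart to it. Counting every incarceration then adds one event to the baseline side for each such patient whose episode falls within the preceding 12 months. With each patient as their own control, nothing in the design separates that fall from a program effect.

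The effect on the correctional system is a stated purpose of the study (Protocol section 3), and 7.1 anticipates a net-benefit calculation. An artefact in the custody count would carry into both. Leaving the rule open also allows the count to be chosen after the data are seen.

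**Working it through.** **The plan's own figure.** N = 32 (Protocol 7.2) comes with no effect size, event rate, standard deviation or power, so it cannot be reproduced.

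**Inputs from the documents.** N = 32; significance level 0.05 (7.3, taken as two-sided); 12 months on each side (4.2).

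**Assumptions, none from the documents.** There is no program effect. The mean rate is L = 0.5 incarcerations per year in both years, with a range of 0.25 to 1.0. Rates vary between patients as a gamma distribution with shape 1, and counts are Poisson given the rate. A paired t test stands in for the planned MANCOVA or multi-level model. Results are from simulation.

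**Mechanism A: the episode is an extra event that triggers entry.** Let q be the share of patients with such an episode in the baseline year. The expected baseline count is L + q and the expected follow-up count is L. The false fall is q, or q/(L + q) in relative terms.

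| L | q | Relative fall | Chance of a false significant fall |
|---|---|---|---|
| 0.5 | 0 | 0 | about 2.5% |
| 0.5 | 0.10 | 0.10/0.60 = 17% | 8% |
| 0.5 | 0.25 | 0.25/0.75 = 33% | 26% |
| 0.5 | 0.50 | 0.50/1.00 = 50% | 70% |
| 0.25 | 0.50 | 0.50/0.75 = 67% | 89% |
| 1.0 | 0.50 | 0.50/1.50 = 33% | 46% |

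Without variation between patients, the L = 0.5 results for q = 0.10, 0.25 and 0.50 are 7.5%, 24% and 69%, so the gamma term matters little. Excluding the episode restores q = 0.

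**Mechanism B: a share s of patients is selected for having at least one baseline incarceration, which did not itself trigger entry.** With L = 0.5 and shape 1:

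- Chance of no baseline incarceration: 1/(1 + 0.5) = 0.667. Chance of at least one: 0.333.
- Mean baseline count in selected patients: 0.5/0.333 = 1.5.
- Mean true rate in selected patients: (1 + 1.5) × 0.5/1.5 = 0.833.
- Counting everything: a false fall of 1.5 − 0.833 = 0.667 per selected patient.
- Dropping one episode: 1.5 − 1 = 0.5 against 0.833, a false rise of 0.333 per selected patient.

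| s | Mean fall, all counted | False significant fall | Mean rise, one dropped | False significant rise |
|---|---|---|---|---|
| 0.25 | 0.167 | 14% | 0.083 | 6% |
| 0.50 | 0.333 | 37% | 0.167 | 13% |

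**Reading the two together.** The full count leans toward the program under both mechanisms. The count without the episode is unbiased under A and leans against the program under B. Reported side by side, the two expected changes bracket zero when the program does nothing.

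**The case against.** The strongest reply is that the wording does not create the bias. In a population with frequent justice contact, the entry episode may itself be a re-incarceration, so changing one word in 7.1 would not exclude it. That stands: what is missing is a counting rule, and the mismatch in terms shows that none was set.

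A reader might infer that the entry rule builds an extra incarceration into every patient's baseline, which would make a false positive nearly certain. The documents do not support this. The criteria in 5.1 are joined by and/or, so hospital or crisis use can suffice. Forensic patients include people found Not Criminally Responsible or Unfit (2.1), and justice involvement is not the same as custody.

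A reader might also infer that a counting rule removes the problem entirely. Mechanism B shows that it can reverse the bias, and selection for frequent contact leaves regression to the mean whatever is done with one episode.

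Timing is open too. Eligible patients are already in the program. If the index date is study enrollment, the entry episode of a long-standing client may predate the baseline year, and part of that year may be program time, which pulls the other way.

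Finally, the percentages follow from an assumed share and rate, and the paired t test is not the planned model. They are illustrations, not properties of this trial. None of these points supplies the missing rule.

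**Conclusion.** The point holds in conditional form. The endpoint and the analysed variable carry different names, neither is defined, and the plan as written counts entry-related custody on the baseline side only. For each patient whose entry followed an incarceration in the 12 months before the index date, this pushes the comparison toward the program.

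The direction is clear for those patients. The size is not, because the documents give neither their share nor the rate, and the undefined index date could offset part of the effect. Under the stated assumptions at 0.5 per year, shares of 25% and 50% give a false significant fall in about 26% and 70% of trials if the episode triggers entry, and about 14% and 37% if patients were merely selected for having one.

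**What to change.** 1. Use one defined term for the custody outcome in Protocol 4.1, Protocol 7.1 and the SAP.
2. Set the index date as the date of entry into the dispensing program, with 12 months on each side.
3. Flag the incarceration, if any, that directly led to entry, using a rule fixed before outcomes are seen.
4. Report the before/after change both excluding and including the flagged episode. Claim a reduction in re-incarcerations only if it holds with the episode excluded.
5. Apply the same rule to a hospital admission that led to entry.

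This needs no new patients or visits: it takes SAP wording and one flag per patient, since justice contacts and hospital records are already to be obtained. The costs are fewer baseline events and wider intervals, a judgement in flagging the episode (the documents do not say whether the records show what led to entry), and a possible bias against the program where the episode did not itself trigger entry. The rule does not remove the remaining regression to the mean, which should be stated as a limitation.

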7.3 The level of significance to be used for any differences

p < 0.05

7.4 Criteria for the termination of the study.

Timeframe of study = approximately one year.

7.5 Procedure for accounting for missing, unused, and spurious data.

Cleaning data, missing data analyses and manual review of data collected etc.

7.6 Procedures for reporting any deviation(s) from the original statistical plan (any deviation(s) from the original statistical plan should be described and justified in protocol and/or in the final report, as appropriate).

All deviations from the statistical plan will be based on the quality of data collected during the study and will be filed as amendments to the protocol with the Ethics Board.

7.7 The selection of subjects to be included in the analyses (e.g., evaluable subjects).

Participants who are currently part of the Forensics program and who are enrolled in the daily dispensing program and have participated in the program for at least one month will be included in the analyses.

8 Ethics

Description of ethical considerations relating to the study.

Ethical considerations relating to the study are that participants may be part of a vulnerable population, and participant characteristics need to be considered as well, such as First Nations individuals. Moreover, the participants are also patients of the principal investigator. To address this issue, the principal investigator will not discuss the study with participants, and will neither encourage nor discourage participation. All study contact will be with a research assistant who is not involved in patient care.

9 Data Handling and Record Keeping

All the data will be maintained in a Redcap database with only authorized individuals having access. All data used for analysis will be stripped of personal identifiers and only aggregate data will be reported.

10 Publication Policy

Publication policy, if not addressed in a separate agreement

Appendix 1: Client Self- Reported Measure Instrument Version 1 August 04 2017*

	True	False	Don't Know
1. I feel free to do what I want about taking medication	[]	P1 []	[]
2. People try to force me to take medication	N2[]	[]	[]
3. I have enough of a chance to say whether I want to take medication	[]	V3[]	[]
4. I choose to take medication	[]	P[]	[]
5. I get to say what I want about taking medication	[]	V[]	[]
6. People threaten me to get me to take the medication	N[]	[]	[]
7. It is my idea to take the medication	[]	P[]	[]
8. Someone physically tries to make me take the medication	N[]	[]	[]
9. No one seems to want to know whether I want to take the medication	[]	[]	[]
10. I am threatened with commitment (being sectioned)	N[]	[]	[]
11. They say they would make me take the medication	N[]	[]	[]
12. No one tries to force me to take the medication (R)	[]	N[]	[]
13. My opinion about taking the medication doesn't matter(R)	V[]	[]	[]
14. I have a lot of control over whether I take the medication	[]	P[]	[]
15. I have more influence than anyone else on whether I take the medication	[]	P[]	[]
16. How does being prescribed the medication make you feel? Does it make you feel:	[]	[]	[]
Angry	[]	[]	[]
Sad	[]	[]	[]
Pleased	[]	[]	[]
Relieved	[]	[]	[]
Confused	[]	[]	[]
Frightened	[]	[]	[]

Perceived coercion	/5
Negative pressures	/6
Voice	/3

(*) adapted from The MacArthur Coercion Study Admission Experience Survey (AES, short form, 16 items)

(1) Perceived coercion subscale: items scored as false=1; true/don't know=0

(2) Negative pressures subscale: items are scored as true=1; false/don't know=0 (except item 12 which is reverse scored)

(3) Voice subscale: items scored as false=1; true/don't know=0 (except item 13 which is reverse scored)

(R) Reverse scored for subscale analysis

2. Please describe any major differences that you have noticed in the transition from before the daily dispensing project began to after its onset.

Please read the following statements and rate your level of agreement with each item:

3. The new program makes medication adherence more likely to occur.

Not applicable?/ Unable to answer	Strongly disagree	Disagree	Neutral	Agree	Strongly Agree
--------------------------------------	-------------------	----------	---------	-------	-------------------

4. This new program is feasible for all clients.

Not applicable?/ Unable to answer	Strongly disagree	Disagree	Neutral	Agree	Strongly Agree
--------------------------------------	-------------------	----------	---------	-------	-------------------

5. The new program alleviates pressure for mental health inpatient and crisis services.

Not applicable?/ Unable to answer	Strongly disagree	Disagree	Neutral	Agree	Strongly Agree
--------------------------------------	-------------------	----------	---------	-------	-------------------

6. The new program alleviates pressure from the correctional system.

Not applicable?/ Unable to answer	Strongly disagree	Disagree	Neutral	Agree	Strongly Agree
--------------------------------------	-------------------	----------	---------	-------	-------------------

7. The new program is more cost-effective for the mental health system.

Not applicable?/ Unable to answer	Strongly disagree	Disagree	Neutral	Agree	Strongly Agree
--------------------------------------	-------------------	----------	---------	-------	-------------------

8. My workload has increased as a result of the new program.

Not applicable?/ Unable to answer	Strongly disagree	Disagree	Neutral	Agree	Strongly Agree
--------------------------------------	-------------------	----------	---------	-------	-------------------

If yes, please briefly describe: _____

9. The new program provides notable benefits to me.

Not applicable?/ Unable to answer	Strongly disagree	Disagree	Neutral	Agree	Strongly Agree
--------------------------------------	-------------------	----------	---------	-------	-------------------

If so, please describe these benefits.

10. The new program provides disadvantages to me.

Not applicable?/ Unable to answer	Strongly disagree	Disagree	Neutral	Agree	Strongly Agree
--------------------------------------	-------------------	----------	---------	-------	-------------------

If so, please describe these disadvantages.

11. The new program provides notable benefits to clients.

Not applicable?/ Unable to answer	Strongly disagree	Disagree	Neutral	Agree	Strongly Agree
--------------------------------------	-------------------	----------	---------	-------	-------------------

If so, please describe these benefits.

12. The new program provides disadvantages to clients.

Not applicable?/
Unable to answer

Strongly disagree Disagree Neutral Agree Strongly Agree

If so, please describe these disadvantages.

13. In your opinion, what has worked well in the new program?

14. In your opinion, what has NOT worked well in the new program?

15. Overall, how satisfied are you with the new program?

Not applicable

Very Dissatisfied

Dissatisfied

Neutral

Satisfied

Very
Satisfied

16. Please provide suggestions for improving the new daily dispensing program (e.g., ways to improve efficiency, feasibility, cost-effectiveness, benefit the client, etc.)

17. In your opinion, does this program improve public safety?

Yes

(please explain why)

No

(please explain why not)

Appendix 3: Client Satisfaction Measure 1

Patient Satisfaction Survey*:

Hello, my name is [name] and I wanted to ask you a few questions regarding the Daily Dispensing program that you are involved in. We are doing an evaluation of this program and we'd like to ask for your help with this evaluation by doing a short survey on what you felt while going to the program. The survey takes about 10-15 minutes and is voluntary. All of your answers will be kept separate from the program. Your taking part in the program is not affected by your choice to answer or not to answer this survey. Will you be able to answer a few questions?

If YES: <Proceed with the survey>

If NO: "Thank you for your time." Do you have any further questions?

Instructions for answering the survey

I will give you a number of statements and I would like you to let me know how much you agree with each statement on a scale of 0 to 10 with 0 being 'do not agree at all' and 10 being 'completely agree'.
(If ≤ 4 ask to explain rating and enter under comments)

*adapted from Patient Satisfaction Survey CoaguCheck INR, used by Centre for Healthcare Innovation (CHI) to assess patient satisfaction

			Rating 0 to 10 0= not at all 10=fully agree	Comment (if ≤4 enter why here)
Accessibility	1	The hours of the program were convenient.		
	2	I found it easy to get the care that I needed.		
	3	It was convenient to get my medications delivered to me.		
Availability of resources	4	I was able to contact the program easily when I needed to.		
	5	The wait times to get into the program were short.		
Continuity of care	6	It was easy to get a referral when I needed one.		
	7	My doctor knew what was happening with me at the program during my regular visit.		
Outcome of care	8	Participation in the program helped me to improve my overall health.		
	9	I am able to better manage my condition.		
	10	The program made it less likely for me to have to go to the hospital emergency room.		
	11	The program made it less likely that I will get in trouble with the law.		
	12	The program met my needs.		
Humanness	13	The program staff listened to my problems.		
	14	The program staff spent the right amount of time with me.		
	15	The program staff were caring and responsive to my needs.		
Information gathering	16	The program staff kept my information private/confidential.		
	17	I did not need to repeat my information at different departments in the program.		
Information giving	18	The advice I got from the program staff was good for my condition.		
	19	The staff fully answered all of my questions.		
	20	I had all the information I needed to decide to participate in the program.		
	21	I knew what I was signing up for when I agreed to participate in the program.		
Pleasantness of surroundings	22	The program staff were courteous and friendly.		
Quality and/or competence	23	The program staff were competent.		
	24	The quality of my medical care was ... (poor to excellent)		
	25	My overall satisfaction with the program is...		
	26	How likely would you be to recommend this program to others?		
Open Ended questions	27	What are some of the things that you liked about participating in the program?		
	28	What are some of the things that made it hard for you to participate in the program?		
	29	In what way could we improve the program?		

Thank you for taking the time to participate in this survey!

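### The client satisfaction form has no 'not applicable' code, and its agreement scale does not fit items 24 to 26, so some ratings will be hard to interpret

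*Protocol*

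**What the plan says.** Protocol section 4.1 includes in its primary-endpoint sentence "well as participants' perceptions of coercion with regards to taking part in the program and satisfaction with the program". Section 7.1, repeated in the SAP, gives the analysis: "Descriptive statistics would be used to elaborate on patient satisfaction and other variables of interest". Neither document states a total or domain score, or a rule for an unanswered satisfaction item.

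Appendix 3 is an interviewer-read survey with 26 rated items and three open questions (27 to 29).

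- **Scale.** Clients are asked to rate each statement "on a scale of 0 to 10 with 0 being 'do not agree at all' and 10 being 'completely agree". The form's column header gives similar agreement anchors. No other response is printed.
- **Probe.** The interviewer's instruction is "If ≤ 4 ask to explain rating and enter under comments". The comment column repeats it: "Comment (if ≤4 enter why here".
- **Conditional items.** Item 6 reads "It was easy to get a referral when I needed one". Item 4 likewise assumes that the client had a need to contact the program, and item 17 assumes dealings with more than one department.
- **Closing items.** Item 24 asks about quality of care and prints a poor-to-excellent range. Item 25 is the stem "My overall satisfaction with the program is", left open. Item 26 asks how likely the client would be to recommend the program.

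The other two instruments do provide a way out. The client coercion measure (Appendix 1) has a 'Don't Know' column with a scoring rule, and the stakeholder survey (Appendix 2) offers "Not applicable?/ Unable to answer".

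**The concern.** Satisfaction is reported as raw ratings. Service use has a 12-month baseline for each patient (section 4.2), but satisfaction is surveyed only among participants in the new program, with no stated earlier measure or comparison group. An artefact of the form therefore has nothing to cancel against.

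Three features deserve attention. A number given for an experience that never occurred looks like any other rating and cannot be separated later. A single agreement scale leaves the end points of the quality, overall-satisfaction and recommendation items to the interviewer or the client. A request to explain that is attached only to low ratings makes those ratings a little more burdensome to give. At stake is how far individual item results, including the overall item, can be read at face value. Section 3 also intends to use client feedback to improve the program.

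**Working it through.** The plan gives no figure for satisfaction that could be reproduced. The check is a reading of the form, followed by an illustration of size.

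**1. Do the printed response options cover the items?**

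| Items | What the item needs | What the form gives |
|---|---|---|
| 4, 6, 17 | A code for clients without the experience | 0 to 10 only |
| 24 | Quality anchors tied to numbers | Poor-to-excellent wording, not mapped to 0 to 10, alongside an agreement scale |
| 25 | Satisfaction anchors | An open stem with no anchors of its own |
| 26 | Likelihood anchors | Agreement anchors; the column header's 'not at all' could serve as the lower end, but the upper end does not fit |

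The closing items are 3 of the 26 rated items. The stakeholder survey's own overall item (item 15) runs from very dissatisfied to very satisfied with a 'not applicable' choice, so a suitable format already exists within the protocol.

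**2. Effect of a missing 'not applicable' code.**

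Input from the documents: N = 32 (section 7.2). Assumptions: all 32 respond; the mean is 8 among clients to whom the item applies; m clients lack the experience but each give the rating f.

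Item mean = ((32 − m) × 8 + m × f) / 32

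| m | f = 0 | f = 5 | f = 10 |
|---|---|---|---|
| 3 | 232/32 = 7.25 | 247/32 = 7.72 | 262/32 = 8.19 |
| 6 | 208/32 = 6.50 | 238/32 = 7.44 | 268/32 = 8.375 |
| 10 | 176/32 = 5.50 | 226/32 = 7.06 | 276/32 = 8.625 |

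The error can go either way. With a code and exclusion, the mean would be 8.00 in every row, on 29, 26 or 22 clients.

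**3. Effect of the one-sided probe, if there is one.**

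Assumption: k of the 32 clients raise a rating to 5 to avoid the question.

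Fall in the share rated 4 or below = k / 32. Rise in the item mean = k × shift / 32.

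- k = 1, moving from 4 to 5: share falls 1/32 = 3.1 points; mean rises 0.031.
- k = 4: share falls 4/32 = 12.5 points; mean rises from 4 × 1/32 = 0.125 (4 to 5) to 4 × 5/32 = 0.625 (0 to 5).
- k = 8: share falls 8/32 = 25 points; mean rises from 0.25 to 1.25.

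The documents give no information on k, and k = 0 is possible. The share rated 4 or below is used here only to show scale; it is not a planned outcome.

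**The case against.** The strongest reply is that little depends on this. Satisfaction is descriptive, has no test or threshold and does not enter the MANCOVA. That stands and keeps the point minor. It does not remove the point, because in a descriptive analysis the ratings themselves are the result.

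A reader might infer that the form pushes satisfaction upward. The documents do not support that. Only the probe could act in that direction, and its effect is conjecture. The missing code and the ill-fitting anchors have no fixed direction. There are also safeguards: section 8 assigns all study contact to a research assistant outside patient care, clients are told that answers are kept separate from the program and that taking part in it is unaffected, and items 27 to 29 ask everyone what they liked, what was hard and what to improve.

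A reader might also infer that clients are forced to give a number. Nothing says so. The survey is voluntary, a cell could be left blank, and section 7.5 mentions missing-data analyses in general terms. The gap is narrower: no code is printed, and no rule separates 'does not apply' from 'unanswered'.

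Nor is item 24 without anchors. It has verbal ones that are not tied to the numbers.

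Finally, asking why an item was rated low serves the stated aim of improving the program. Deleting the probe would lose those reasons, so the documents do not support removing it.

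**Conclusion.** The point holds as a minor measurement issue. Two defects can be verified on the page: no 'not applicable / don't know' code where at least items 4, 6 and 17 need one, and no fitting 0 to 10 anchors for items 24 to 26. They make those ratings hard to interpret without biasing them in a known direction. In the illustration with 6 inapplicable answers among 32, the item mean ranges from 6.50 to 8.375 around 8.00. That range rests on an assumed number of such clients, an assumed mean and full response. The anchor problem cannot be expressed in points.

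The one-sided probe is a possible, unquantified source of upward bias that the study's safeguards partly offset. It does not justify saying that the endpoint is inflated. Nor do these defects imply that item 25 should become the single reported satisfaction result; the documents do not rank the items, and that would be a separate choice of endpoint.

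**What to change.** Amend Appendix 3 as follows.

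1. Add a 'not applicable / don't know' code to each rated item. Leave those answers out of that item's denominator and report how many there were.
2. Before items 24 to 26, have the interviewer read item-specific anchors: item 24, 0 = poor to 10 = excellent; item 25, 0 = very dissatisfied to 10 = very satisfied; item 26, 0 = not at all likely to 10 = extremely likely.
3. Optionally, invite a comment whatever the rating. This makes the probe symmetric and keeps the explanations of low ratings.

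The cost is a short form and script change filed with the Ethics Board, slightly smaller denominators for some items and, if step 3 is adopted, possibly a slightly longer interview. No extra participants are needed, the same interviewer can carry it out, and the service-use and incarceration analysis does not change.
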